13.3 Confidentiality of Data and Access to Subject Records

Prior to initiation of the trial, the Investigator will sign a fully executed confidentiality agreement with Sanofi Pasteur.

^a Unless the electronic medical records are managed by validated computerized systems that are compliant with US 21 CFR Part 11, in which case they are acceptable on their own.

Sanofi Pasteur personnel (or designates), the IRBs, and regulatory agencies, including the FDA, require direct access to all study records, and will treat these documents in a confidential manner. In the event a subject's medical records are not at the investigational site, it is the responsibility of the Investigator to obtain those records if needed.

13.4 Monitoring, Auditing, and Archiving

13.4.1 Monitoring

Before the start of the trial (i.e., before the inclusion of the first subject in the first center), the Investigators and the Sponsor's staff or a representative will meet at the site-initiation visit to discuss the trial protocol and the detailed trial procedures. Emphasis will be placed on promoting understanding of inclusion and exclusion criteria, visit timing, safety procedures, informed consent procedures, SAE reporting procedures, eCRF completion, and the handling of samples and products. The Sponsor's staff or a representative will ensure and document that all material to be used during the trial has been received at the site; and that the study investigator team and local Sponsor/delegate staff have been properly informed about the trial, GCP and regulatory requirements, and the Sponsor's procedures. Specific training sessions for the study investigator team and the CRAs on these topics may be performed as necessary, and should be documented.

The following instruction manuals will be provided: the eCRF Completion Guidelines for entering data into the eCRF, and the Operating Guidelines for detailing trial procedures such as those related to product management and the handling of samples.

After the start of the trial, the Sponsor's staff or a representative will be in regular contact with the investigational team through telephone calls and regular follow-up visits. The Investigator or delegate must be available for these visits and must allow the Sponsor/delegate staff direct access to subject medical files and eCRFs. During these visits, the Sponsor/delegate staff will:

- Evaluate the quality of the trial progress (adherence to protocol and any study-specific guidelines, quality of data collection and document completion, presence of appropriate signatures on consent forms, occurrence of SAEs, sample and product management, cold-chain monitoring, archiving)
- Source-verify completed eCRFs and any corresponding answered queries
- Determine the number of complete or ongoing issues identified at monitoring visits (e.g., protocol deviations, SAEs). Any identified problems will be discussed with the Investigator, and corrective or preventive actions will be determined, as appropriate.
- After all protocol procedures have been completed and the data have been entered into the eCRF, the Investigator must still be available to answer any queries forwarded by the Sponsor. All data-related queries must be completed prior to database lock.

At the end of the trial, a close-out visit will be performed to ensure that:

- The center has all the documents necessary for archiving
- All samples have been shipped to the appropriate laboratory (GCI)
- All unused materials and products have been either destroyed or returned to the Sponsor

13.4.2 Audits and Inspections

A quality assurance audit may be performed at any time by the Sponsor's Clinical and Medical Quality Operations Department or by independent auditors to verify that the trial has been conducted according to the protocol, GCP and ICH requirements, and other applicable regulations. An inspection may be conducted by regulatory authorities. The Investigator must allow direct access to trial documents during these inspections and audits.

13.4.3 Archiving

The Investigator must keep all trial documents after the completion or discontinuation of the trial, whatever the nature of the investigational center (private practice, hospital, or institution), for as long as required by applicable laws and regulations. In the absence of any applicable laws or regulations, trial documents will be kept at a minimum for the duration indicated on the Clinical Trial Agreement (CTA). In no event, should study personnel destroy or permit the destruction of any trial documents upon less than 90 days advance written notification to the Sponsor. In addition, trial documents should continue to be stored, at Sponsor's sole expense, in the event that the Sponsor requests in writing that such storage continues for a period of time that exceeds that required by any applicable law or regulation or the CTA. The Investigator will inform Sanofi Pasteur of any address change or if they will no longer be able to house the trial documents.

Archived data may be held on electronic records, provided that a back-up exists and that a hard copy can be obtained if required. The protocol, documentation, approvals, and all other documents related to the trial, including certificates attesting that satisfactory audit and inspection procedures have been carried out, will be kept by the Sponsor in the Trial Master File (TMF). Data on AEs are included in the TMF. All data and documents will be made available if requested by relevant authorities.

13.5 Financial Contract and Insurance Coverage

A CTA will be signed by all the parties involved in the trial's performance, if relevant. The Sponsor has an insurance policy to cover any liabilities that may arise from use of the product and/or the study protocol.

13.6 Stipends for Participation

Subjects may be provided with a stipend according to local practice to compensate for the time and travel required for study visits and procedures.

## List of Abbreviations

ACIP	Advisory Committee on Immunization Practices
AE	Adverse Event
AR	Adverse Reaction
BL	Blood Sample
CBER	Center for Biologics Evaluation and Research
CDC	Centers for Disease Control and Prevention
CDM	Clinical Data Management
CI	Confidence Interval
CSR	Clinical Study Report
DC	Diary Card
dil	Dilution
eCRF	Electronic Case Report Form
FAS	Full Analysis Set
FDA	Food and Drug Administration
GBS	Guillain-Barré Syndrome
GCI	Global Clinical Immunology
GM	Geometric Mean
GMT	Geometric Mean Titer
HAU	Hemagglutination Unit
HAI	Hemagglutination Inhibition
IRT	Interactive Response Technology
LLOQ	Lower Limit of Quantification
MD	Missing Data
MedDRA	Medical Dictionary for Regulatory Activities
NM	Non-Measurable
PPAS	Per-Protocol Analysis Set
PT	Preferred Term
RBC	Red Blood Cell
RCDC	Reverse Cumulative Distribution Curve
SAE	Serious Adverse Event
SafAS	Safety Analysis Set
SAP	Statistical Analysis Plan
SD	Standard Deviation
TLF	Table(s), Listing(s), and Figure(s)

ULOQ                      Upper Limit of Quantification  
WHO                        World Health Organization

## 1 Introduction

This is a trial evaluating the safety and immunogenicity in children of 2 different dose levels of the 2016–2017 formulation of quadrivalent inactivated influenza vaccine (Fluzone® Quadrivalent, Influenza Vaccine). To assess whether a higher dose of Fluzone Quadrivalent vaccine might induce a more robust antibody response (and potentially offer improved protection) among children 6 through 35 months of age, this trial will compare the safety and immunogenicity of a full dose (15 µg HA per strain in 0.5-mL volume) of the vaccine versus a half dose (7.5 µg HA per strain in 0.25-mL volume).

Because children 6 through 23 months of age are at substantially increased risk for influenza-related hospitalizations, and children 24 through 59 months of age are at increased risk for influenza-related clinic and emergency department visits, the Advisory Committee on Immunization Practices (ACIP) has recommended annual vaccination of all eligible children in these age groups. In recent years, ACIP has further expanded the targeted age groups, and now recommends that all eligible people 6 months of age and older receive annual influenza vaccination (1) (2). The ACIP continues to emphasize the importance of vaccinating persons  $\geq$  6 months of age who have high-risk medical conditions (1)

If a child 6 months through 8 years of age is receiving influenza vaccine for the first time, based on ACIP recommendations, 2 doses of influenza vaccine should be administered during the current season. This recommendation is based on studies demonstrating that vaccine effectiveness is lower among children who have never received influenza vaccine previously or who received only 1 dose in their first year of vaccination than it is among children who received 2 doses in their first year of being vaccinated. Children 6 months through 8 years of age who are adequately primed, based on influenza vaccination history, should receive 1 dose during the current season as per ACIP recommendations (1) (2).

Vaccine efficacy and effectiveness studies have generally demonstrated that inactivated influenza vaccines reduce influenza disease in children, but in some studies the effectiveness in children 6 through 35 months of age is lower than that in children 3 years of age and older. The practice of administering a half-dose of inactivated influenza vaccine to young children originates from experience with whole-virus vaccine, which was reactogenic and frequently caused fever in young children. Split-virus and subvirion influenza vaccines are less reactogenic and data from the studies cited above support the safety of the full-dose in this population. Further, data from recent studies suggest that in children 6 through 35 months of age, full-dose influenza vaccine induces generally higher antibody responses compared to those induced by half-dose vaccine, without causing materially higher rates of systemic or injection site reactions. In most studies, differences in antibody responses between the full- and half-dose groups were greatest in the youngest age cohorts (i.e., 6- through 11-month-old or 6- through 23-month-old children).

[REDACTED]

[REDACTED]

Based on the foregoing, there is a strong rationale to allow use of the 0.5-mL dose for young children. Consequently, the purpose of the study described herein is to describe the safety and immunogenicity of the 0.5-mL dose (15 µg HA per strain) of Fluzone Quadrivalent vaccine in children 6 through 35 months of age, with the intent to modify the vaccine's Prescribing Information (Dosage and Administration) to show the 0.5-mL dose of Fluzone Quadrivalent vaccine as indicated for all ages 6 months and older, including children 6 months through 8 years of age (who might receive 1 or 2 doses as recommended by the ACIP).

[REDACTED]

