A 2012 systematic review of published studies estimated vaccine effectiveness among healthy children was 40% (95% CI: 6%–61%) for those aged 6 through 23 months and 60% (95% CI: 30%–78%) for those aged 24 through 59 months (15). During the 2010–2011 season, when all 3 vaccine virus strains appeared antigenically similar to circulating strains, vaccine effectiveness was assessed among children in a large multi-site observational study (16). Vaccine effectiveness among children aged 6 months through 2 years was 58% (95% CI: 31%–74%) and the effectiveness among children aged 3 through 8 years was 69% (95% CI: 56%–77%).

To evaluate whether a higher dose might induce a more robust antibody response (and potentially offer improved protection) among children 6 through 35 months of age, investigators have evaluated the safety and immunogenicity of a full dose (15 µg HA per strain in 0.5-mL volume) versus a half dose (7.5 µg HA per strain in 0.25-mL volume).

Skowronski and colleagues evaluated 252 previously unimmunized children 6 through 23 months of age who were randomly assigned to receive 2 doses administered 4 to 6 weeks apart of full-dose (15 µg HA per strain) or half-dose (7.5 µg HA per strain) trivalent inactivated influenza vaccine (IIV3) during the 2008–2009 season (17). Children administered full-dose IIV3 responded with higher geometric mean HAI antibody titers to all 3 vaccine components compared to those who received half-dose IIV3. In addition, seroprotection and seroconversion rates were higher among children 6 through 11 months of age who received the full-dose vaccine. For example, seroprotection rates ranged between 40% and 55% in the half-dose group and between 70% and 75% in the full-dose group. Rates of fever were not higher among full- versus half-dose recipients. Rates of injection site reactions were lower in the half-dose group, but the differences between groups were not statistically significant.

Esposito and colleagues investigated full-dose (15 µg HA per strain) versus half-dose (7.5 µg HA per strain) virosomal-adjuvanted subunit IIV3 (2008–2009 season) administered 4 weeks apart to 65 previously unvaccinated children 6 through 35 months of age (18). Following the first dose, HAI titers were significantly higher in the full-dose group compared with the half-dose group for

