## 2.2 Secondary Objective

To compare antibody responses induced by the 0.5-mL dose of Fluzone Quadrivalent vaccine to those induced by the 0.25-mL dose of Fluzone Quadrivalent vaccine as assessed by geometric mean titer (GMT) ratios and seroconversion rate differences after the final vaccination in subjects 6 to < 36 months of age.

The endpoints for the secondary objectives are presented in [Section 4.2](#).

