## 5.1.2.2 Statistical Methods

### 5.1.2.2.1 Geometric Mean Titers

The statistical methodology will be based on a 2-sided 95% CI of the ratio of the GMTs (0.5-mL dose divided by 0.25-mL dose) at 28 (window, 28–35) days after the final vaccination.

Non-inferiority for GMTs will be demonstrated if the lower limit of the 2-sided 95% CI of the GMT ratio is > 0.667 for each of the 4 virus strains (A/H1N1, A/H3N2, B1 and B2). The 95% CI will be calculated using normal approximation of log-transformed titers.

For the separately virus strain (A/H1N1, A/H3N2, B1 and B2), the primary parameter will be the difference of the means of the log10-transformed post-vaccination titers between GMT0.5mL and GMT0.25mL.

Each hypothesis will be supported by the data if the upper bound of the calculated 95% CI is > 0.667. This is the equivalent to testing the null hypothesis using a 1-sided type I error rate of 0.025.

For each virus strain (A/H1N1, A/H3N2, B1 and B2), the null hypothesis and the alternative hypothesis, are:

$$H_0: \text{GMT}_{0.5\text{mL}} / \text{GMT}_{0.25\text{mL}} \leq 0.667$$

$$H_A: \text{GMT}_{0.5\text{mL}} / \text{GMT}_{0.25\text{mL}} > 0.667$$

or equivalently,

$$H_0: \log_{10}(\text{GMT}_{0.5\text{mL}}) - \log_{10}(\text{GMT}_{0.25\text{mL}}) \leq \log_{10}(0.667)$$

$$H_A: \log_{10}(\text{GMT}_{0.5\text{mL}}) - \log_{10}(\text{GMT}_{0.25\text{mL}}) > \log_{10}(0.667)$$

For the separately considered GMT hypotheses, if the null hypothesis is rejected, then the alternative hypothesis of non-inferiority will be supported.

The 2-sided 95% CI for the ratio of GMTs (GMT0.5mL / GMT0.25mL) will be calculated using normal approximation of log-transformed concentrations.

The 95% CI for the GMT ratio between 2 groups will be constructed as follows: Logarithm transformation of the individual concentrations will be calculated. Assuming that individual log10 (concentration) is normally distributed, the 95% CI for the difference in log10 (GMT) between 0.5-mL (or Groupi) and 0.25-mL (or Groupj) will be in the form:

$$\bar{X}_i - \bar{X}_j \pm t(1-\alpha/2, n_i + n_j - 2) \times S \sqrt{1/n_i + 1/n_j}$$

where  $\bar{X}_i = \log_{10}$  (GMC) is the mean of log10 (concentration) of Group *i*,

$S^2 = [(n_i - 1) S_i^2 + (n_j - 1) S_j^2] / (n_i + n_j - 2)$  is the pooled sample variance,

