#### 5.1.2.2.2 Seroconversion

The statistical methodology will be based on a 2-sided 95% CI of the difference in seroconversion rates (0.5-mL dose minus 0.25-mL dose) at 28 (window, 28–35) days after the final vaccination. Non-inferiority for seroconversion will be demonstrated if the lower limit of the 2-sided 95% CI is  $> -10\%$  for the 4 strains (A/H1N1, A/H3N2, B1 and B2). The 95% CI of the rate difference will be computed using the Wilson Score method without continuity correction.

For each virus strain (A/H1N1, A/H3N2, B1 and B2), the null hypothesis and the alternative hypothesis, are:

$$H_0: P_{0.5mL} - P_{0.25mL} \leq -10\%$$

$$H_A: P_{0.5mL} - P_{0.25mL} > -10\%$$

For the separately considered seroconversion hypotheses, if the null hypothesis is rejected, then the alternative hypothesis of non-inferiority will be supported.

The CI of the difference in proportions  $P_{0.5mL} - P_{0.25mL}$  will be computed using the Wilson Score method without continuity correction, quoted by Newcombe (3).

For descriptive purposes, the statistics presented in Table 5.1 will be produced.

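### The SAP's introduction asks whether the higher dose gives a stronger antibody response, but the visible plan tests only non-inferiority, so a gain could be described but not concluded with pre-specified error control

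*SAP*

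**What the plan says.** The SAP's section 1 (Introduction) gives the reason for comparing the full and half doses in this trial as "To assess whether a higher dose of Fluzone Quadrivalent vaccine might induce a more robust antibody response". It later summarises earlier studies as suggesting that "full-dose influenza vaccine induces generally higher antibody responses compared to those induced by half-dose vaccine", and then says that "the purpose of the study described herein is to describe the safety and immunogenicity of the 0.5-mL dose", with a labelling change in view. The secondary objective in SAP 2.2 takes no direction: "To compare antibody responses induced by the 0.5-mL dose of Fluzone Quadrivalent vaccine to those induced by the 0.25-mL dose".

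The tests are one-directional:

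- **GMT (SAP 5.1.2.2.1):** "Non-inferiority for GMTs will be demonstrated if the lower limit of the 2-sided 95% CI of the GMT ratio is > 0.667". All four strains must meet this.
- **Seroconversion (SAP 5.1.2.2.2):** "Non-inferiority for seroconversion will be demonstrated if the lower limit of the 2-sided 95% CI is" greater than -10%, for the four strains.

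Protocol 12.1.2 has the same hypotheses. In both SAP sections, rejecting the null supports non-inferiority and nothing more. The visible text has no superiority hypothesis, decision rule or multiplicity rule.

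**The concern.** The case for doubling the antigen is a better response, but the confirmatory tests ask only whether the response is not much worse. A GMT ratio with a lower limit of 0.70 passes, although it is compatible with a full-dose GMT 30% below the half-dose GMT. If the trial does show a gain, the plan gives no basis for stating it as a conclusion.

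Eight intervals will be reported (four strains, two endpoints). Without a rule fixed in advance, it is easy to pick out whichever ones exclude 1 or 0 and present them as evidence of a stronger response. The error rate of that reading is not controlled.

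**Working it through.** **1. The plan's own error rate.** SAP 5.1.2.2.1 says of the GMT criterion: "This is the equivalent to testing the null hypothesis using a 1-sided type I error rate of 0.025". This reproduces: 1 - Φ(1.96) = 0.025. The subset of about 1600 (800 per arm) cannot be reproduced, because SAP 5.5 and protocol 12.5 are redacted.

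**2. One strain, one endpoint.** If the true ratio is 1, the chance that the 95% lower limit exceeds 1 is 0.025. A lower limit above 1 is necessarily above 0.667, so testing superiority after non-inferiority leaves the non-inferiority error unchanged. To this extent the step costs no alpha.

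**3. Several strains.** With all true ratios equal to 1:

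- Any of four strains, independent: 1 - 0.975^4 = 0.096.
- Any of eight comparisons, independent: 1 - 0.975^8 = 0.183.
- A simulation of 400,000 trials (non-inferiority required on all four GMTs, then superiority; SD 0.6, 680 per arm) gives the figures below.

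| Correlation between strains | Any of 4, unadjusted | Any of 4, Holm | All 4 required |
|---|---|---|---|
| 0 | 0.096 | 0.025 | 0.000 |
| 0.3 | 0.087 | 0.024 | 0.000 |
| 0.5 | 0.078 | 0.022 | 0.001 |
| 0.7 | 0.064 | 0.018 | 0.003 |

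Requiring all four strains needs no adjustment under any configuration. A false claim requires a strain with no gain to pass its own 0.025 test.

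**4. Holm does not use the ordinary 95% CI.** Its first step is at one-sided 0.025/4 = 0.00625, z = 2.498, which corresponds to a two-sided 98.75% interval.

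**5. Power for GMT superiority.** Assumed: 700 evaluable per arm out of the 800 planned; log10 SD 0.5 to 0.7. SE = SD × √(2/700). Ratio detectable with 90% power = 10^((z + 1.2816) × SE).

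| SD | SE | z = 1.960 | z = 2.498 (first Holm step) |
|---|---|---|---|
| 0.5 | 0.0267 | 1.22 | 1.26 |
| 0.6 | 0.0321 | 1.27 | 1.32 |
| 0.7 | 0.0374 | 1.32 | 1.38 |

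**6. Power for seroconversion superiority.** Assumed: half-dose rate 40% to 60%, gain 7.5 points, 700 per arm. At 40%, SE = √((0.40 × 0.60 + 0.475 × 0.525)/700) = 0.0264. Power = Φ(0.075/0.0264 - 1.96) = 0.81. Over the range it is 0.81 to 0.83 unadjusted and 0.63 to 0.67 at the first Holm step.

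**7. Passing the non-inferiority gate, true difference zero, 700 per arm.**

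- GMT: Φ(0.1759/SE - 1.96), where 0.1759 = -log10(0.667), is at least 0.997 per strain.
- Seroconversion: Φ(0.10/√(2p(1-p)/700) - 1.96) is 0.96 to 0.97 per strain for p of 40% to 60%. For all four strains it is 0.86 to 0.88 if independent.

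The ample margin therefore belongs to GMT. Seroconversion has less to spare.

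**8. Cost of the all-four rule.** With 680 per arm, a true ratio of 1.3 in every strain and independence, power for all four is 0.95, 0.78 and 0.53 for SD 0.5, 0.6 and 0.7. Per-strain power at the first Holm step is 0.96, 0.84 and 0.69.

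**The case against.** The strongest reply is that the design is coherent as it stands. The formal objectives compare or describe, and none promises superiority. The stated purpose is descriptive and supports a labelling change, for which non-inferiority on fever and antibody response is a sensible basis. In protocol 1.4, the wording about a more robust response belongs to earlier work, in which "investigators have evaluated the safety and immunogenicity of a full dose" against a half dose. The SAP sentence may simply be a loose paraphrase of it. This stands: the mismatch comes from one introductory sentence, and the non-inferiority design is not at fault.

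Two stronger readings are tempting, and the documents do not support either.

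- *A reader might infer that the trial cannot answer its own question.* The SAP plans 95% CIs for every GMT ratio and seroconversion difference, together with fold-rises and reverse cumulative distribution curves, so a gain would be visible. What is missing is a pre-specified, error-controlled conclusion.
- *A reader might infer that a superiority step is free.* That is true for one strain and endpoint, or if all four strains must pass. Separate claims by strain need a multiplicity rule.

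It is also fair to say that an addition to the SAP alone would leave it at odds with the protocol, whose hypotheses are non-inferiority only. The reply does not remove the fact that the SAP states the question as this trial's own and gives no rule for answering it.

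**Conclusion.** The point holds in a limited form. The visible plan lets a higher antibody response be described but not concluded with error control. Unadjusted reading of the four GMT intervals would raise the one-sided error from 0.025 to about 0.064 to 0.096, the range running from a between-strain correlation of 0.7 to independence.

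A gated superiority step is feasible at the planned size for GMT ratios of roughly 1.2 to 1.4. It is weaker for seroconversion, where a 7.5-point gain has only 0.63 to 0.67 power at the first Holm step. These power figures rest on the assumed 700 per arm, the SDs and the rates. The redacted sections and the separate table shells might contain a superiority or multiplicity rule, so the finding is confined to the text that can be read. It is an inexpensive pre-specification that was left out, and it does not affect the validity of the non-inferiority tests.

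**What to change.** Before unblinding, amend SAP 5.1.2.2 and mirror the change in protocol 12.1.2.

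1. First correct SAP 5.1.2.2.1, which also says a GMT hypothesis is supported if the upper bound of the CI exceeds 0.667. This contradicts the lower-limit rule in the same section and should refer to the lower limit.
2. Gate: non-inferiority shown for all four strains on both GMT and seroconversion.
3. Then test GMT superiority (ratio above 1) by strain with Holm at one-sided 0.025, using Holm-adjusted limits or p-values and not the unadjusted 95% CIs.
4. Test seroconversion superiority (difference above 0) in the same way, only if all four GMT superiority tests succeed.

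A simpler alternative to steps 3 and 4 is to claim GMT superiority only if the ordinary 95% lower limit exceeds 1 for all four strains. It needs no alpha adjustment but gives up claims on single strains. If the sponsor wants no superiority claim, the SAP's introductory sentence should be aligned with protocol 1.4, and the SAP should say that any higher response is descriptive.

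The cost is a short addition to both documents, with no extra subjects or data and no change to the non-inferiority error. The downside is a formal claim that may fail for some strains.
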